Appendix L: Data Log

Two data logs will be used in each park (or four during reliability data collection periods). The first page (Parks Data Log) summarizes data collection to date, while the second (Park User Interview Log) and subsequent pages are used to record daily park user interviews.

PARKS DATA LOG
 ____ of ____

Park: _____

Name	Date & Day of week	Park interviews		Household interviews		Station interviews	
		iPad	Paper	iPad	Paper	iPad	Paper
Sub-total							
TOTALS							

Park User Interview Log

Park name: _____

Date: _____

Promotora name: _____

#	Target Area	Gender M = Male F = Female	Race/Ethnicity L = Latino B = Black W = White O = Other	Age Group Ad = Adult Sr = Senior	Activity Level S = Sedentary A = Active	Outcome I = iPad P = Paper R = Refuse	Comments
1		M F	L B W O	Ad Sr	S A	I P R	
2		M F	L B W O	Ad Sr	S A	I P R	
3		M F	L B W O	Ad Sr	S A	I P R	
4		M F	L B W O	Ad Sr	S A	I P R	
5		M F	L B W O	Ad Sr	S A	I P R	
6		M F	L B W O	Ad Sr	S A	I P R	
7		M F	L B W O	Ad Sr	S A	I P R	
8		M F	L B W O	Ad Sr	S A	I P R	
9		M F	L B W O	Ad Sr	S A	I P R	
10		M F	L B W O	Ad Sr	S A	I P R	
11		M F	L B W O	Ad Sr	S A	I P R	
12		M F	L B W O	Ad Sr	S A	I P R	
13		M F	L B W O	Ad Sr	S A	I P R	
14		M F	L B W O	Ad Sr	S A	I P R	
15		M F	L B W O	Ad Sr	S A	I P R	

At the end of the day, record the number of park user interviews completed in each category. Add the sub-total from the preceding day to your daily total, and enter the sum in the appropriate sub-total box.

[figure not shown]
	Female		Male	
	Sedentary	Active	Sedentary	Active
Daily total				
Sub-total				

Note that this page is to be duplicated for each day of data collection (i.e., each data collector should complete one of these pages for each day of data collection in every park. A single packet can be made with one Parks Data Log followed by six park user interview logs (possibly more for makeup days).

[figure not shown]

Promoting Physical Activity in High Poverty Neighborhoods

NCT # NCT01925404

September 26, 2017

Data analyses

We first conducted descriptive analyses of park characteristics, park baseline observation data, and characteristics of resident survey respondents. To obtain community level population data we used census data and GIS methods to calculate population density and socio-demographic characteristics of the population within a one-mile radius of each park (USCensus, 2010a, 2010b). We calculated the violent crime rate in the park neighborhoods (1-mile radius around the study parks) using a City of Los Angeles Police Department publicly available dataset (DataLA, 2016). We also summarized process measures for the intervention by study arms. We then conducted formal statistical analyses of park use outcomes and survey data. The primary pre-specified outcome was estimated energy expenditure in parks from the SOPARC observations using MET scores, the ratio of work metabolic rate to standard resting metabolic rate. We assigned MET levels of 1.5 for sedentary, 3 for moderate, and 6 for vigorous activity as identified by Ainsworth et al (Ainsworth et al., 2000). The secondary outcome measure was the number of observed park users. Survey outcomes included self-reported park use (number of visits in past seven days, duration of park visits, awareness of park programs, having participated in park programs), perception of park safety, and number of weekly exercise sessions.

We fitted difference-in-differences (DID) models between the two measurement waves and four study arms (Yang & Tsiatis, 2001). The effect of the intervention was modeled as the wave by study arm interaction. All models used random effects to account for intra-class correlation within each park as well as fixed effects to account for observation times (time of day, weekend versus weekdays). This approach can eliminate temporal trends unrelated to the intervention and is particularly suitable for this study due to the relatively long observation periods. We also included indicators for park cohorts to account for potential seasonal effects.

We used negative binomial distributions in the DID models due to the sizable heteroscedasticity in park use outcomes (Cohen et al., 2012). Effects of the intervention were presented in the scale of multiplicative scale (i.e., % changes) in these models. We also examined the outcomes by two age groups (youths versus adults). In analyzing survey outcomes, we controlled for respondent-level covariates to reduce estimation biases because randomization was not at the individual level, including gender, age, education level, obesity status, address buffer (<.25 mile, .25 to .5 miles, and .5 miles to 1 mile to park), self-rated health, perception of park safety, primary language, and having children under 18 years old. All statistical models were fitted in SAS 9.4. We also conducted sensitivity analyses using robust standard errors for park clustering effects and alternative scale for transformed mean outcomes (log or logit) wherever appropriate. The main findings were not sensitive to alternative model specifications.

Statistical power: This study was powered to detect a small to medium standard effect size under the regular setting of two-sided p -value <0.05 and power >0.80 . With 12 parks in each study arm and the extensive repeated measurements in each park (18 hourly observation per wave for two waves), we can detect a difference of 0.34 times standard deviation (SD) between any two arms when the intra-class correlation is no greater than 0.10. Based on historic data from previous studies (average park use 55 persons/hour, $SD=35$, approximately)(Cohen et al., 2013) meant that we could detect an additional 11.9 persons/hour. Because most survey outcomes were categorical, we used a two-sample z -test for calculating the detectable effect size for survey analysis. With 20 surveys in each wave and in each park's neighborhood, we could detect a difference of 15 percentage points for a binary outcome with a baseline prevalence between 20% and 80%. The detectable effect size is even smaller if the baseline prevalence rate is very high or very low (e.g. $<20\%$, or $>80\%$).

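### If each park keeps one cohort, the cohort indicators cannot adjust the wave-by-arm effect for seasonal change that differs between cohorts

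*SAP*

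**What the plan says.** All of this is in the SAP, Data analyses, unless noted.

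- Effect: "The effect of the intervention was modeled as the wave by study arm interaction". There are two waves and four arms, and the park-use outcomes are fitted with negative binomial models.
- Season: "We also included indicators for park cohorts to account for potential seasonal effects". The other time terms named are time of day and weekend versus weekday. No cohort-by-wave, month or season term is named.
- Claim for the approach: "This approach can eliminate temporal trends unrelated to the intervention".
- Clustering: "All models used random effects to account for intra-class correlation within each park". Whether this means a park intercept alone, or also a park-by-wave effect, is not stated.
- Sensitivity: "We also conducted sensitivity analyses using robust standard errors for park clustering effects", with the result that "The main findings were not sensitive to alternative model specifications".
- Planning: 12 parks per arm, 18 observations per park per wave, and a detectable difference of 0.34 SD "between any two arms when the intra-class correlation is no greater than 0.10".

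The Protocol (Data Collection) spreads a park's three weekdays and three weekend days over five to six months, with three observations a day. That gives 6 × 3 = 18, matching the SAP. Every scan carries a date (Protocol, Park scan form). Appendix K makes the park the unit of randomization. Neither document defines the cohorts or gives their number, the wave dates, or the allocation of arms within cohort.

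**The concern.** The estimated effect is a difference between arms in within-park change. A covariate that takes the same value in both waves shifts both by the same amount and drops out of the change. The SAP recognises season as a threat and gives the cohort indicators the task of dealing with it. On the ordinary meaning of a park cohort, they can absorb level differences between cohorts but not differences in how cohorts changed. Suppose one cohort's waves ran from a cool to a warm season and another's did not, and the arms were unevenly spread over those cohorts. The seasonal difference would then enter the wave-by-arm estimate. Each wave's five to six months averages out part of this but does not span a year. At stake are the error rate and precision of the primary test.

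**Working it through.** **Layout and the plan's own figure.** Take total variance 1, ICC r = 0.10, 12 parks per arm and 18 observations per wave. For a difference-in-differences model with a park intercept, the SE of a contrast of two arms is √(4(1 − r)/(12 × 18)) = √(3.6/216) = 0.129. The detectable difference is 2.80 × 0.129 = 0.362 SD. The SAP states 0.34 SD, which is 0.34 × 35 = 11.9 persons/hour. Baseline-adjusted park means give 0.330 (z) to 0.338 (t, 44 df). The layout is therefore close to the planned one. The SAP's mean of 55 and SD of 35 describe park users ("The secondary outcome measure was the number of observed park users"). No mean, SD or ICC is given for the primary MET outcome.

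**Do the indicators move the effect?** In linear mixed fits they changed the wave-by-arm estimate by less than 10⁻¹⁴. In random-intercept negative binomial fits at mean 55 and SD 35, adding indicators for four cohorts moved the log rate ratio by a median of 0.0005 to 0.0019 (maximum 0.014), against an SD of the estimate of 0.08 to 0.09. Over assumed coefficients of variation of 0.4 to 1.0, the median move was at most 0.005 (maximum 0.033, in a setting where that SD was 0.133).

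**Size of the unadjusted change (all shifts assumed).** Let four equal cohorts have wave 2 minus wave 1 shifts evenly spaced from −s to +s, allocated without regard to arm, with no park drift. The variance of the shifts over 48 parks is S² = (48/47)(5/9)s² = 0.567s². This adds (2/12)S² to the variance of the contrast, which is 0.01667 without shifts.

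| s (SD) | persons/hour (× 35) | added variance | SD of estimate | type I error, model SE (simulated) |
|---|---|---|---|---|
| 0.1 | 3.5 | 0.00095 | 0.133 | 5.6% |
| 0.2 | 7.0 | 0.00378 | 0.143 | 7.5% |
| 0.3 | 10.5 | 0.00851 | 0.159 | 10.8% |

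For example, at s = 0.3: √(0.01667 + 0.00851) = 0.159. Alternating −s/+s shifts gave 6.2, 9.7 and 15.0%. Over 2, 3, 4 and 6 cohorts the ranges were 5.4–6.2%, 7.1–9.8% and 10.0–15.3%. The mean estimate was about 0 in every run. With arms balanced within cohort there was no inflation (4.7–4.9%).

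**What robust SEs recover.** In the unstratified four-cohort runs, park-level SEs held the error rate at 4.9–5.1%, but the SD of the estimate stayed as tabulated. Cohort-by-wave terms give 0.134, close to 0.129 × √(44/41). Excess width is 0.143/0.134 − 1 = 7% at ±0.2 SD and 0.159/0.134 − 1 = 19% at ±0.3 SD. At ±0.1 SD, 0.133 against 0.134 is no gain.

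Park drift shrinks the benefit. If a share f of the ICC is wave-specific, the contrast variance before cohort shifts is (2/12) × 2 × (rf + (1 − r)/18).

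- f = 0.2: variance 0.0233, and 0.0233 × 44/41 = 0.0250 with cohort-by-wave terms. The SD ratios are √(0.0271/0.0250) = 1.04 and √(0.0318/0.0250) = 1.13, so the excess is 4% and 13%.
- f = 0.5: variance 0.0333, and 0.0358 with the terms. The ratios are √(0.0371/0.0358) = 1.02 and √(0.0418/0.0358) = 1.08, so the excess is 2% and 8%.

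With arms balanced within cohort, park-level SEs without cohort-by-wave terms are conservative (4.4, 3.0 and 1.5% at ±0.1, 0.2 and 0.3 SD). With the terms they give 4.9%.

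**The case against.** The strongest reply is that nothing here is shown to have happened. The SAP says only that the indicators account for potential seasonal effects, and they do absorb level differences between cohorts. Fixed membership is an inference from the phrase. If both waves of each cohort fell in the same season, the difference within park cancels season. If arms were balanced within cohort, the error rate is not inflated. The SAP also reports robust SEs for park clustering and unchanged main findings. All of that stands, and it limits the consequence mainly to precision. It does not supply an adjustment for change that differs by cohort.

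Two stronger readings are tempting. One is that season biased the effect. A particular uneven allocation could shift a particular estimate, but park-level randomization makes that variance, not systematic bias, and the documents report no imbalance. The other is that the primary SE omits park-specific change between waves. That follows only if the random effect is a park intercept alone. Type I error at ICC 0.10 would then be 7.2, 9.4 or 15.4% with 10, 20 or 50% of the ICC wave-specific. The SAP's single ICC is compatible with that structure but does not establish it, and the robust-SE analysis covers the resulting error in the SE.

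**Conclusion.** The point holds conditionally. If a park keeps its cohort across waves, the indicators have essentially no influence on the effect of interest, and the statement about eliminating temporal trends is right only for trends that cohorts share. The cost arises if cohorts' seasons changed differently between waves. With arms not balanced within cohort, it is a modest rise in the model-based error rate and, after robust SEs, some lost precision once cohort shifts exceed about ±0.1 SD. With arms balanced, it is conservative park-level SEs.

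The sizes rest on assumed shifts, four equal cohorts, ICC 0.10 and a linear approximation to a negative binomial model. They could be negligible. The unstated cohort definition, wave dates, allocation within cohort and random-effects structure are matters to clarify, not demonstrated errors. Severity is minor to moderate.

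**What to change.** Replace the cohort indicators with cohort-by-wave fixed effects, or with calendar month of observation, since scans are dated. Base inference on park-clustered SEs with a small-sample correction (for park-level change, 48 − 4 = 44 df, or 41 with four cohorts), or on a park-by-wave random effect. Make both changes together, because park-level SEs alone are conservative when arms are balanced within cohort. Report the refit beside the existing model and label it as made after results were known. State the cohort definition and number, wave dates, allocation within cohort and random-effects structure. If each cohort's waves matched in season, saying so would settle the seasonal point.

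The cost is a refit with no new data and a few degrees of freedom. The SD of the estimate rises from 0.129 to 0.134 with four unstratified cohorts and no drift, and does not rise if arms are balanced within cohort. Intervals widen if parks drift.

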While routine physical activity is critical to optimal health, our preliminary studies have indicated that residents of low-income communities in Los Angeles are less likely to exercise than those in high-income communities, and they are less likely to use their neighborhood parks, even when the parks are within walking distance. Parks in low-income neighborhoods tend to be smaller and serve a greater population density, but even after accounting for the size and the population served, they are still used less than parks in wealthier neighborhoods. In our preliminary studies, we found that parks in low-income neighborhoods also had fewer part-time staff and offered fewer programs and organized activities than parks in higher-income areas, and these factors partly accounted for their lower use. As well, parks in low-income neighborhoods are often perceived as less safe, a characteristic associated with lower use. Simultaneously, the lack of use and dearth of programming may contribute to a perception of lack of safety, creating a vicious cycle. Nonetheless, we have documented that when parks in low-income neighborhoods offer events and activities, they can be just as busy as parks in higher-income areas. We hypothesize that limited park use in low-income areas can be attributed to the lack of organized and reliable infrastructure of activities that meet the needs of local residents and that offering more activities and programs in parks will increase park use and park-based physical activity.

According to the Task Force on Community Level Preventive Services, community-level campaigns are both effective and scalable. For the past eight years, we have conducted research in public neighborhood parks and found that these venues offer great potential for increasing physical activity for populations. Based upon this work, as well as our previous work on the cost-effectiveness of physical activity interventions, we propose to test community-level campaigns targeting low-income populations that will be relatively low-cost and easy to replicate.

The study has three specific aims:

1. Using a full factorial design, compare whether park use and population physical activity in low-income neighborhoods increase with the availability of a) more organized physical activity classes, including Zumba, line dancing, and aerobics indoors and outdoors, and/or b) a loyalty program approach that rewards frequent park users.

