2. Determine whether either of these two approaches changes the perception of park safety and neighborhood safety.
3. Identify the cost effectiveness of both approaches in terms of dollars spent to generate increased physical activity in parks as measured through systematic observation.

This manual describes study protocols and instruments specific to this study. The full SOPARC manual is not included here; however, a brief summary of how it is implemented is described in the Data Collection section. Similarly, only the steps in Pendragon Forms VI that necessary for project functioning are described here. The full manual is available for download from the vendor website (<http://www.pendragonsoftware.com/>).

EQUIPMENT

To accomplish the goals stated above, we will use several different data collection instruments loaded onto a single device. Some of these instruments will be accessed via Pendragon Forms VI, while others are standalone applications developed by RAND for this project. The third party software and hardware used are described briefly below. Each will be discussed in greater detail in later sections describing their use.

Apple iPad Mini

All data collection instruments will be fielded on this device. These are 16GB, WiFi-enabled (i.e., no data plan) devices. Each Mini includes one USB wall charger. Manuals and other documentation are available online.

These devices are not linked to an iTunes or iCloud account, email account, or calendar. Data collectors should be instructed not to link them to any accounts or access iTunes or iCloud on these devices. RAND has logged each of these devices and has the serial numbers and equipment numbers on file.

Setup and daily care

These devices are not to be opened in any way, and settings should be managed by the project manager only. Outside of settings that affect immediate use (e.g., brightness, volume) field staff should be instructed not to alter settings to avoid any interruption of Pendragon or the other project applications.

iPads are to be charged the night before use in the field using the Apple charger only. Whenever possible a surge protector should be used.

Pendragon Forms VI

This software allows the user to create custom data collection forms that are output in HTML5 applications that run while disconnected from a network. Data collected on the handhelds are synchronized into Microsoft Access. All data will be entered in one of five forms created in this application.

Park Counters

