Appendix C: Park user and household survey (English)

Revised 6/11/13

NEIGHBORHOOD PARKS

Interviewer: _____ Date: _____ Time: _____ AM / PM (Circle one)

Participant type: Park user ¼ mile resident ½ mile resident 1 mile resident
 Station ¼ mile Station ½ mile Station 1 mile

Gender: Male Female Age: _____ Activity level: Sedentary Active

INTERVIEWER TO READ STATEMENT: This survey is mainly about _____ [park name]. Please think about this park when you answer the questions.

1. How many children under the age of 18 do you have?

_____ (insert number)

2. How do you describe yourself in terms of race or ethnicity? (Check one)

- Latino Asian / Pacific Islander
- White American Indian / Alaska Native
- Black Other _____

3. How often do you come to this park? (Check one)

- Daily
- A few times a week
- Once per week
- A couple times per month
- Monthly
- A few times a year
- This is the first time
- Never [skip to #10]

4. How many times did you visit this park within the past SEVEN days?

_____ (insert number)

- Don't know

5. On a typical day when you go to the park, how long do you stay there?

(Check one)

- 0-30 minutes 2 – 3 hours
- 31-60 minutes > 3 hours
- > 1 hour, but < 2 hours

6. When was the first time you came to this park?

(Check one)

- Today
- This month
- In the past 6 months
- Between 6 - 11 months ago
- Between 1 - 2 years ago
- More than 2 years ago

7. How do you usually get to the park?

(Check one)

- Walk
- Bike
- Car
- Bus or other public transportation
- Other _____

8. What do you usually do while at this park?

(Check all that apply)

- Aerobics Meet friends
- Baseball/softball Playground
- Basketball (indoors) Sitting in park
- Basketball (outdoors) Skating
- Celebrations or picnics Soccer
- Classes Swimming
- Frisbee Tennis
- Gymnasium activity Volleyball
- Gymnastics equipment Walking
- Handball Walking with dog
- Other _____

9. When you are at this park, do you run into people you know? (Check one)

- Yes, often Rarely
- Yes, sometimes No, not at all

10. If you do not visit this park, why not?
(Only ask this question if the respondent answered "Never" to question 3)

11. How would you grade the park staff with respect to their helpfulness, friendliness, and professionalism?
(Check one)

A D
 B F
 C Don't know the staff

12. In general, how safe do you feel the park is?
(Check one)

Very safe
 Safe
 Not very safe
 Not safe at all

13. Where do you usually exercise? *(Check one)*

I don't usually exercise
 Park
 Home

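### The survey models adjust for perceived park safety, itself an Aim 2 outcome, so the self-reported park use coefficients are not total intervention effects if safety changes

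*SAP*

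**What the plan says.** The Data analyses section of the SAP gives perceived park safety two roles. The list of survey outcomes ends with "perception of park safety, and number of weekly exercise sessions". The paragraph on modeling then says that survey outcomes were adjusted for respondent-level covariates, to limit bias because parks and not individuals were randomized. That covariate list ends with "self-rated health, perception of park safety, primary language, and having children under 18 years old". The intervention effect is the wave-by-arm interaction.

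The protocol makes safety a target of the trial. Specific aim 2 is: "Determine whether either of these two approaches changes the perception of park safety and neighborhood safety". Its background section says that "parks in low-income neighborhoods are often perceived as less safe, a characteristic associated with lower use", and that "the lack of use and dearth of programming may contribute to a perception of lack of safety, creating a vicious cycle".

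Safety is item 12 of the survey in Appendix C ("In general, how safe do you feel the park is"), the form that also asks about visits in the past seven days (item 4) and length of stay (item 5). The interviewer tells respondents that their answers are anonymous, and Appendix K says that the data carry no personal identifiers.

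The only robustness checks that the SAP names are "sensitivity analyses using robust standard errors for park clustering effects and alternative scale for transformed mean outcomes (log or logit"). It does not mention a model without the safety covariate.

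**The concern.** A covariate that the intervention may alter does not only remove confounding. It can also remove part of the effect being estimated. The protocol's rationale allows for this: scarce programming may lower perceived safety, and lower perceived safety goes with lower use. Extra classes could raise use partly by making the park feel safer. A model that holds safety fixed leaves that part out.

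Readers will take the wave-by-arm coefficients for self-reported park use as what the interventions did in total. If safety changed, these coefficients answer a narrower question. If unmeasured factors drive both safety ratings and park use, they do not isolate a clean direct effect either.

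A null result for Aim 2 would not clear the adjustment. The SAP's planning figure for the survey is that "we could detect a difference of 15 percentage points for a binary outcome with a baseline prevalence between 20% and 80"%. A shift of 5 to 10 points could go undetected and still move the other coefficients.

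The SAP also does not say that safety leaves the covariate list when it is the outcome. It presumably does, but the text should say so.

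**Working it through.** **1. Is the rating post-intervention?** Safety serves as both outcome and covariate in models spanning the two waves, so it was collected in both. Only wave 2 values follow the intervention, and these feed directly into the wave-by-arm coefficient. With anonymous interviews, no identifiers and no described linkage, a wave 2 respondent has no baseline rating that could be used instead.

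**2. The SAP's 15-point figure.** There are 12 parks × 20 surveys = 240 respondents per arm per wave. A two-sample z-test without clustering has power of at least 0.91 for 15 points at baseline prevalences of 20% to 80%. Its smallest detectable increase at 80% power is 11.1 points from a 20% baseline and 12.7 points from 50%. So a shift of 10 points or less falls below the detectable size even before clustering is allowed for.

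**3. How much the adjustment can remove.** The documents give none of the inputs, so all are assumptions on a linear scale:

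- a = rise in the share who feel safe
- b = visits per week attributable to feeling safe
- d = direct effect, in visits per week
- c = amount by which an unmeasured common cause inflates the safety coefficient (c = 0 for pure mediation)

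The formulas are:

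- total effect = d + ab
- adjusted coefficient = d − ac
- share lost = a(b + c)/(d + ab)

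Worked example with a = 0.15, b = 0.5, d = 0.10, c = 0: ab = 0.075, the total is 0.175, the adjusted value is 0.100, and 0.075/0.175 = 43%.

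Share of the total effect lost under pure mediation:

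| d | b | a = 0 | 5 points | 10 points | 15 points |
|---|---|---|---|---|---|
| 0.30 | 0.25 | 0% | 4% | 8% | 11% |
| 0.30 | 0.50 | 0% | 8% | 14% | 20% |
| 0.30 | 1.00 | 0% | 14% | 25% | 33% |
| 0.20 | 0.25 | 0% | 6% | 11% | 16% |
| 0.10 | 0.50 | 0% | 20% | 33% | 43% |
| 0.05 | 0.50 | 0% | 33% | 50% | 60% |

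With a common cause, at a = 0.15, b = 0.5, d = 0.10:

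- c = 0.08: 0.15 × 0.58/0.175 = 50%
- c = 0.16: 0.15 × 0.66/0.175 = 57%
- c = 0.25: 0.15 × 0.75/0.175 = 64%
- c = −0.25: 0.15 × 0.25/0.175 = 21%

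**4. Simulation check.** A two-arm, two-wave linear simulation used 20 replicates of 200,000 records, with 50% feeling safe at baseline, a = 0.15, b = 0.5 and d = 0.10.

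- Without a common cause, the coefficient fell from 0.176 to 0.101 on adjustment (formula: 0.175 to 0.100).
- With a common cause that moved the probability of feeling safe by ±10 points and visits by ±0.4, the safety coefficient rose from 0.50 to 0.66. The effect estimate fell from 0.174 to 0.075 (formula: 0.10 − 0.15 × 0.16 = 0.076).
- At a = 0, the adjusted and unadjusted estimates agreed (0.101) in both settings.

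**The case against.** The strongest reply has five parts.

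- **Scope.** Energy expenditure and observed user counts come from SOPARC observation, not from the survey. Only the survey outcomes are affected, and only if safety changed. This stands and limits the weight of the point.
- **Assumed sizes.** Every input is chosen, and the largest losses pair small direct effects with large safety shifts. A negative c shrinks the loss. This stands: the figures show what is possible and do not estimate what happened.
- **Scale and feedback.** The SAP calls most survey outcomes categorical and mentions log and logit scales. Logit coefficients can change when a predictive covariate is added even if safety did not move. The background also lets low use feed back into perceived safety, in which case the simple mediation formula does not apply. Both are valid cautions about the arithmetic and about reading two models side by side. Neither supports conditioning on an Aim 2 outcome.
- **Respondent mix.** There are 20 surveys per park neighborhood per wave, and convenience station interviews can replace household ones. The mix may therefore differ between waves, and safety may partly correct for that. This is possible, but gender, age, education, address buffer, language and children remain in the model to address mix.
- **Timing.** The SAP reports completed analyses, so replacing the main survey model now is post hoc. That calls for disclosure and for showing both models.

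**Conclusion.** The concern holds. Perceived park safety is an outcome that the trial set out to change, and its wave 2 value is conditioned on when effects on the other survey outcomes are estimated. If safety changes, those coefficients are not total effects. No sensitivity analysis named in the SAP tests this, so its statement that the main findings were robust to other specifications does not settle it.

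The overlap of roles is certain from the text. The size and direction of the bias are not known. The illustrative losses rest on a linear scale, assumed values of a, b, c and d, and no feedback from use to safety. With no change in safety there is no bias from this source on that scale. The point deserves correction because it governs how the self-reported park use results are read, but it does not touch the trial's primary or secondary outcome.

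**What to change.** - Refit the survey models without perceived park safety and make these the main survey analysis.
- Keep the safety-adjusted models only as a labeled mediation or sensitivity analysis, and report the two side by side. Where a logit scale is used, note that the coefficients can differ without any mediation; differences in predicted probabilities are easier to compare.
- State that safety is not a covariate in the model for safety itself.
- Disclose that the change was made after the analysis.

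The cost is one refit with a covariate removed, one extra column in the survey results and a sentence of disclosure. Some reduction in residual variance is lost, probably slight, as is whatever correction for respondent mix the safety item supplied. Reporting both models lets readers judge the second.
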